*Network modeling* is ideally suited for analysis of risk of disease transmission in complex systems (1), and can account for symptom latency, changes in classroom group composition, and student mobility. Agent based models (ABMs) developed from network models can be used to study time varying outcomes arising from changes in behavior (e.g. vaccine acceptance), immunity, and asymptomatic infection among students, teachers and staff. This approach enables *in silico* evaluation of hypothetical testing strategies, simulation of infection dynamics, and assessment of alternative mitigation strategies. [name] has developed network models and analytics for risk of transmitted infection in a complex, high contact hospital environment (1), and [name] is currently creating ABMs that assess strategies to decrease COVID-19 infection risk on the UR Undergraduate Campus. Analytic approaches based on our prior work (1-6), will be used to construct (1) a network model of who is in contact with whom, for how long and (2) a mobility model of individual's travel between school locations and (3) agent based models of behavior, given data about anxiety, vaccine status, and adherence to guidelines. The **contact network**, will model testing strategies for surveillance for new infections in a mix of individuals with varying levels of immunity, vaccine acceptance, exposure, and new emerging viral strains. The **mobility network** will be used to model prevention strategies of changing staff and student classes/movement/interaction to decrease the risk COVID-19 transmission. **Agent based models** will test the effects of behaviors on school operations. The number of students and staff who remain on-site and in-school, will be key outcomes. Questions will include: How does the mixture of immunity, class/student scheduling, and vaccine acceptance create opportunities for COVID-19 spread (and control)? Do asymptomatic individuals with positive PCR tests spread virus?

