*Network modeling* – We will contrast both a **contact network** and a **mobility network model (Fig 2)**. Data used for modeling will include the instruction schedules of IDD-students, staff and class locations. Each data record will contain the subject ID, activity, location, time, and duration. Student and staff attributes will be stored in the secure BLIS informatics database system (see Facilities and Resources), which will also hold the COVID-19 PCR and serology testing results. We will also incorporate anxiety data from the PROMIS survey (Goal 5 below), and rates of prior infection/vaccination (derived from serology data). We will use the schedule database to construct directed, bipartite graphs where the nodes represent two categories of individuals (students, staff), and the edges are weighted by the duration of contact (4, 6). A **mobility network model** (1, 2) (**Fig. 2B**) will capture the movement of students and staff between physical locations within the building. For both network models, we will characterize measures of network structure (density, diameter) (1, 4, 6), and identify individuals with high contagion centrality. We will simulate various testing frequencies of asymptomatic individuals (1). For example, we will model outcomes for increasing testing for: (1) staff who contact many students to decrease transmission risk, (2) staff who connect groups of students to decrease between-group spread. Sensitivity analysis will assess how modification of parameters (e.g. vaccination proportion, asymptomatic viral load) affects the ability to detect infection.

[figure not shown]

Figure 2

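### The contact network is specified as a bipartite student-staff graph, so it has no direct student-student or staff-staff edges, although it is meant to show who contacts whom and to guide testing

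*Protocol*

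**What the plan says.** Scientific Goal 3 (protocol section 1.4) plans a contact network, a mobility network and agent-based models. It introduces the first as "a network model of who is in contact with whom, for how long", with no restriction on which pairs count. It gives that network a specific job: it "will model testing strategies for surveillance for new infections in a mix of individuals" who differ in immunity, vaccine acceptance and exposure.

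The Network modeling paragraph then says the team will "construct directed, bipartite graphs where the nodes represent two categories of individuals (students, staff), and the edges are weighted by the duration of contact". The mobility network follows as a separate item, so from context this sentence defines the contact network. On inputs: "Data used for modeling will include the instruction schedules of IDD-students, staff and class locations". Also: "Each data record will contain the subject ID, activity, location, time, and duration".

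Density, diameter and contagion centrality are planned for both networks. Two testing examples are given: more testing of "staff who contact many students to decrease transmission risk", and of "staff who connect groups of students to decrease between-group spread". On robustness: "Sensitivity analysis will assess how modification of parameters (e.g. vaccination proportion, asymptomatic viral load) affects the ability to detect infection".

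The SAP says only that network models and agent-based simulations will be used to try out mitigation strategies. It gives no contact structure.

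**The concern.** In a bipartite graph, edges run only between the two node categories. Two students who share a classroom all day have no edge, and neither do two staff who share a room. That does not fit a network of who contacts whom.

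What is at stake is the guidance on whom to test. On this graph every path from one student group to another must pass through staff. Student-to-student crossings, and crossings that use staff-to-staff contact, are absent by construction. Staff who link groups therefore look like the only gateway. The structural measures shift as well: two students in the same room are at distance 2, not 1. The named sensitivity parameters do not include edge structure, so the planned checks would not reveal the effect.

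**Working it through.** The documents give no figure on this point, so there is none to reproduce. The counts below use protocol figures. The effect sizes use assumed contact patterns and are illustrations.

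**1. Pairs without an edge.** Inputs: 450 students and 500 staff (protocol section 2.1).
- All pairs: 950 × 949 / 2 = 450,775.
- Student-staff pairs: 450 × 500 = 225,000.
- Student-student pairs: 450 × 449 / 2 = 101,025.
- Staff-staff pairs: 500 × 499 / 2 = 124,750.
- Excluded: 101,025 + 124,750 = 225,775, and 225,775 / 450,775 = 50.1%.
- If density uses all pairs as its denominator, it cannot exceed 225,000 / 450,775 = 0.499.

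Many of these pairs may never meet. Within one assumed room of 10 students and 5 staff there are 15 × 14 / 2 = 105 pairs, of which 10 × 5 = 50 have an edge. The other 55 (52%) share the room without one.

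**2. Testing staff who connect student groups.** Assume testing cuts connecting staff's infectiousness by 60%, and that a share f of crossings between groups uses same-category contact that bypasses them. Expected first crossings fall by 0.6 × (1 − f). The bipartite graph forces f = 0:

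| f (assumed) | Fall in expected crossings |
|---|---|
| 0 | 60% |
| 0.25 | 45% |
| 0.50 | 30% |
| 0.75 | 15% |

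For outbreak size, take two assumed rooms, each with 10 students and 5 staff. Four connecting staff split their time equally between the rooms, and one student in room A is the seed. The per-contact transmission probability runs from 0.05 to 0.30. With a 60% cut, room-B student infections fell by about 71% (lowest probability) to 30% (highest) in the bipartite graph, against about 60% to 4% with all edges.

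The low end is noisy because room-B infections are rare there. The leading route is seed, connector, room-B student, with expected count 4 × 10 × (0.05/2)² = 0.025. The cut multiplies this by 0.4 in either graph, a 60% fall. A repeat with 200,000 simulated outbreaks per setting gave 61% in both graphs at 0.05, and 28% against 4% at 0.30. The graphs therefore agree when transmission is low, and the bipartite graph overstates the benefit as transmission rises. In this layout connectors are the only crossing route even with all edges, so the gap comes from spread within rooms alone.

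**3. Testing staff who contact many students.** Assume rooms of 10 students and 5 staff, 100 further staff rotating through 5 rooms each, and a 60% cut in the rotating staff's infectiousness. Contact hours come from shared room slots, and R is the largest eigenvalue of the contact matrix. Added contact has the same hourly rate as student-staff contact.

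| Edges included | Fall in R |
|---|---|
| Student-staff only | 10.3% |
| plus student-student | 5.4% |
| plus staff-staff | 14.9% |
| plus both | 9.1% |

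Over 28 assumed settings (7 room sizes × 50 or 100 rotating staff × 5 or 10 rooms each), the effect relative to the bipartite value was 0.43 to 0.60 with student-student contact added, 1.39 to 1.59 with staff-staff, and 0.66 to 1.07 with both.

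**The case against.** The strongest reply is that this graph is one of three components. The agent-based model allows contact between any agents, will look at how many people occupy a room at once, is meant to explore testing strategies, and can feed back into the network models. The mobility network follows students and staff through shared locations. The sentence on simulating testing frequencies names no graph, and the structural measures are planned for both networks. All of this stands, and it limits the point to work done on the contact network. It does not remove the point. Nothing says the other models supply the missing contacts, and the section also speaks of agent-based models built from the network models, so the restriction could carry over.

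A second reply is that bipartite may be loose wording for two kinds of node. Figure 2 and the cited methods papers were not available, so this cannot be ruled out.

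Two stronger readings are tempting, and neither is supported. A reader might infer that the plan assumes no transmission among students or among staff. The documents never say so, and student-staff-student spread remains in a bipartite graph. A reader might also infer that simulating tests of connecting staff merely returns the assumed effect. That holds for expected first crossings in the bipartite case. It fails for outbreak outcomes: the same 60% cut gave falls well away from 60% as transmission rose. The plan also varies testing frequency rather than fixing a percentage cut.

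**Conclusion.** The point holds for the contact network as written. It has no direct same-category edges, which conflicts with its stated purpose and its role in surveillance testing, and no other text clearly restores them.

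The 50.1% of possible pairs excluded is exact but says nothing about actual contact. The benefit of testing staff who link student groups will tend to be overstated when same-category contact exists, though hardly at all when transmission is low and those staff are the only route between groups. For staff who contact many students the direction is not fixed, and the error may be small if both kinds of same-category contact are similar (9.1% against 10.3% in the main illustration). Every effect size rests on assumed rooms, rotation, rates and a 60% cut, none of which is in the documents.

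This should be corrected before the network is used to decide whom to test. Confidence is medium, because the unseen figure and papers could show that the wording is only loose.

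**What to change.** In the Network modeling paragraph of Scientific Goal 3:

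- Define the contact network as person-to-person, with student-student, student-staff and staff-staff edges derived from shared location and time in the schedule records. Keep student or staff as a node attribute.
- Compute density, diameter, centrality and the testing simulations on that network, and state that the agent-based model uses the same three contact types.
- Add the same-category edge weight to the sensitivity analysis, for example 1, 0.5, 0.25 and 0, where 0 is the graph now described. Report how the result of each testing example changes.
- If bipartite was meant only as two node types, say so in one sentence and confirm that same-category edges exist.

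The cost is analysis code and a few sentences. The planned records already hold person, location, time and duration, and section 4.1 (Other data) says the school will supply room schedules, so classroom edges need no new collection. The downside is that sharing a room only approximates contact, and instruction schedules may miss staff-room and break contacts, so staff-staff edges may be incomplete. State this as a limit.

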## 2. CHARACTERISTICS OF THE RESEARCH POPULATION

### 2.1 Subject Characteristics

All staff and students at Mary Cariola Center (MCC) are eligible for this study

**a) Number of Subjects** – There are 500 on-site staff and 450 students. Up to 950 people may enroll, although we expect around 70% enrollment

**b) Gender and age of subjects** – Among MCC **employees**, approximately 75% are female. We expect at least 50% to consent to testing and another 30% to complete the baseline survey.

**Among students under age 18**, approximately 30% are female, consistent with the national IDD population. We expect 70% to enroll. Unless our enrollment trends show otherwise we do not anticipate any unique messaging or additional outreach to achieve our enrollment target. There are also Mary Cariola students age 18-21 approximately 30% female.

**There are no exclusions by age** however we are limited by the ages of those attending or residing in MCC and the age range of employees.

**MCC students** are included in this study as the main participants as the study seeks to understand testing and transmission patterns among individuals with IDD in school and residential settings including modeling. Most of the students in the school setting are under age 18; The youngest student is age 3. There are also about 60 students at the school between the ages of 18-21. Approximately one third of these students have legally authorized representatives (guardians).

Age distribution of students is:

3-5	20%
6-10	28%
11-14	25%
15-17	19%
18-21	8%

We will track early enrollment to determine if rates are lower than expected or if there are under-represented age groups (based on the age distribution of MCC students). This will warrant revising of recruitment strategies and tactics within the research team and the CAB.

**MCC Staff** range in age from 18 to 75.

STUDY #: 5294

Version Date: 04/17/2023

Page 9 of 27

Efforts to enroll employees will be informed by the CAB. We will track early enrollment to determine if rates are lower than expected or if there are under-represented age groups. Lower than anticipated enrollment will warrant revising of recruitment strategies and tactics within the research team and informed by the CAB.

### **c) Racial and Ethnic Origins**

Underrepresented minorities in the local community are Black and Hispanic. The minority participation in this research among students is based on the distribution of races and ethnicities at Mary Cariola. Thus approximately 43% will be a racial minority (Blacks representing 76%) and 11% will be Hispanic. Materials will be available in Spanish. As part of our vetting process we will assure that the messaging, photos and other representations include minority images and language that reflect health equity.

Among MCC Staff, approximately 30% are Black and 3% are Hispanic.

### **d) Vulnerable Subjects**

This study, by design, involves a vulnerable population, children under age 18. The importance of this study is provided in the application and in the NOSI itself given the risks associated with COVID-19 among this population. The benefits of undergoing testing and the proposed modeling in this group of children considered at high risk for illness and hospitalization due to COVID-19 exposure will be both direct and indirect. First, children will have access to testing not readily available to them. Second, indirect benefits would be the information provided to MCC to modify procedures to mitigate or minimize transmission at the children's residential and school facilities. The proposed testing regime will also help define what pattern of testing is warranted for individuals with IDD. Given the high risk nature of COVID-19 among this population, and the potential for local and national impact, the risks to subjects (primarily discomfort with testing) are reasonable in relation to the importance of the knowledge that reasonably may be expected to result.

### **e) Spanish-speaking Staff and Parents of students**

There are staff at Mary Cariola whose primary language is Spanish. To enroll these participants we will use consent documents and questionnaires translated into Spanish. Additionally, Spanish-speaking members of the study team will consent these participants in Spanish or if necessary we will have translators on-site to facilitate consent in Spanish. Some parents of Mary Cariola students may also have Spanish as their primary language and we will get permission using Spanish and permission and questionnaires translated into Spanish.

## **2.2 Inclusion and Exclusion Criteria**

Criteria are presented below in a table for each of the three groups involved in the study: MCC students, MCC Staff and parent/guardian decision makers.

### **Inclusion and Exclusion Criteria**

Cohort	Study Procedure	Inclusion Criteria	Exclusion Criteria
IDD Students	

COVID-19 RT-PCR Testing

	

IDD Student of the Mary Cariola Center

Age 3 – 21

	

Contraindication to nasal swab

STUDY #: 5294

Version Date: 04/17/2023

Page 10 of 27

	
 
• Anti-SARS-CoV-2 Antibody Testing
 
	
 
• Have a parent/guardian who can give informed consent
 
• In the judgement of the Mary Cariola Medical Staff will be able to safely participate in the study procedures (nasal swab, phlebotomy)
 
	
 
• Contraindication to phlebotomy (e.g. anticoagulated, bleeding diathesis)
 

Mary Cariola Center Staff	
 
• COVID-19 RT-PCR Testing
 
• Anti-SARS-CoV-2 Antibody Testing
 
	
 
• Age 18 – 72
 
• Able give informed consent
 
• Anticipated duration of remaining employment less than 1 month (e.g. retiring)
 
• Must be willing to participate in RT-PCR and antibody testing
 
	
 
• Contraindication to nasal swab
 
• Contraindication to phlebotomy (e.g. anticoagulated, bleeding diathesis)
 

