**Clinical Serological Testing:** Tests with FDA-EUA will be used to assess the presence of IgG antibodies to SARS-CoV-2 (Table 1) every 6 months. Our current Abbott Architect assay qualitatively assesses IgG binding to the SARS-CoV-2 nucleocapsid (NP) protein and we intend to offer the Architect anti-spike (S) semi-quantitative assay when it is granted EUA (expected shortly). Serum will be collected upon enrollment and then every 6 months for the duration of the study period. Assuming 70% study enrollment, this will result in 1,680 staff and 1,330 student serological tests.

[figure not shown]
**Reporting and Result Handling:** The ordering provider ([name]) at the MCC and nursing staff will receive test results. Positive results will be reported to public health agencies via standard clinical protocols. Both molecular and serological *clinical* results will be qualitative (Positive, Negative, Inconclusive). Upon the communication of a positive molecular test result, students and staff will be referred to their primary care providers (PCPs) or urgent care if lacking a PCP. Enrolled study subjects who have been in close proximity to the positive individual will be immediately PCR tested. Unenrolled, exposed individuals will be offered study enrollment or else referred to their PCP/urgent care for testing. RT-PCR positive students will be re-tested every two weeks to assess viral load kinetics.

**Research Serological Testing:** Modeling requires continuous, quantitative data to estimate antibody persistence, and as a correlate of immunity. We will test 200 subjects every 4 weeks for up to 36 months using a multiplex research assay that simultaneously measures IgG levels against the spike (S) and nucleocapsid (N) proteins of SARS-CoV-2 and human seasonal strains (OC43, HKU1, NL63, 229E); we will also measure antibodies directed against the receptor binding domain (RBD) of the S protein. This assay provides absolute measures of serum IgG (ng/ml), and is currently in use in several NIH funded studies (see Fig 1). We are also adding emerging SARS-CoV-2 variants (e.g. UK, South African). Samples will be collected by fingerstick and volumetric micro-sampling (VAMS) to collect 40 $\mu$ l of capillary blood. A topical anesthetic cream can be used prior to collection. Samples will be analyzed by batch in [name] lab.

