### Scientific Goal 2: Serological Testing and Modeling

The dynamics of the immune response to SARS-CoV-2 are as yet unknown in children with IDD, a population with prevalent immunological dysfunction, who may show different COVID-related immunological profiles and latencies to those of the general population. Here, we longitudinally follow those with IDD identified as antibody-positive, from either infection or vaccination, to quantify the timing of reductions in IgG and neutralizing antibody levels. We will use a combination of the SARS-CoV-2 clinical serological assay (described above), and a research multiplex assay for anti-spike and nucleocapsid protein IgG and receptor binding domain (RBS) antibodies, against SARS CoV-2 (including emerging virus variants), and a panel of commonly circulating human coronaviruses. *This will provide serological data uniquely focused on the IDD population with clear implications for public health immunity strategies.*

**Experimental Approach.** IgG responses to individual SARS-CoV-2 antigens (S, NP, RBD) in enrolled students and staff will be measured initially by clinical testing and fingerstick at baseline, and then every four weeks by fingerstick for up to 36 months. Any large increase in anti-SARS-CoV-2 levels will be confirmed by clinical serology. Dynamics of anti-SARS-CoV-2 IgG will be assessed by fitting the anti-S, NP and RBD quantitative results to a modified power law model that accounts for long-term antibody persistence:  $f(t) = k + \log [(1 - \lambda)(c + t)^{-\alpha} + \lambda]$ , where  $k$  is the peak log IgG level,  $\alpha$  is the decay rate,  $c$  is a constant, and  $\lambda$  is the steady-state long-term IgG level. We will fit the model using a mixed effects

**Figure 1 – Serological Testing.** (A) Clinical analysis of persistence of anti-S, anti-NP, and anti-RBD binding IgG and PCR results from the URMC Clinical Laboratory. Note the early decline of anti-NP IgG. (B) Multiplex testing for IgG directed against S proteins for common circulating coronaviruses, including SARS-CoV-2 (SARS2), and prior SARS-CoV-1 and MERS (Middle East Respiratory Virus)

method, where  $k$  and  $\alpha$  are subject specific random effects drawn from a bivariate normal distribution. This will allow comparison of decay rates ( $\alpha$ ) and steady state anti-SARS-CoV-2 IgG levels ( $\lambda$ ) across subjects.

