### **3. SUBJECT IDENTIFICATION, RECRUITMENT, AND CONSENT**

#### **3.1 Method of Subject Identification and Recruitment**

Participants will be assigned de-identified code numbers to maintain confidentiality. This code will be used to label all de-identified documents and data files relating to the subject.

Selection will occur as a function of the criteria above.

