#### **Asymptomatic Testing –**

**Nasal Swab:** Participating individuals (students and employees) will be tested for COVID-19 (RT-PCR) using a specimen collected using a mid-turbinete swab. This asymptomatic testing

STUDY #: 5294

Version Date: 04/17/2023

Page 13 of 27

regime starts on or after (if scheduling testing requires this to begin on a different day) enrollment and is repeated every 5-14 days for up to 36 months. Anyone testing positive is followed up as described below for symptomatic individuals.

**Saliva Sample:** For those participants (students only) that are unable to tolerate the nasal swab (mid-turbinate) test, we will use the Spectrum Solutions™ SDNA-1000 Molecular Diagnostic Saliva Collection Device. This is a self-contained, **EUA authorized** saliva collection system. It requires filling a small tube with saliva.

**Blood Samples:** Participating asymptomatic individuals (students and employees) will be tested for antibodies using the fingerstick upon scheduling first sampling visit and monthly thereafter for up to 36 months. This first blood sampling will be using a fingerstick and 1-2 drops of blood will be collected in a curette for serology testing. Possible complications include pain from the fingerstick, and a low risk of infection. The rationale for this intervention is to measure serum antibodies against SARS-CoV-2 using standard FDA approved testing methods.

A second method for blood sampling using venipuncture will be carried upon enrollment or upon scheduling the first sampling visit and subsequently, every six months for up to 36 months. In addition this method will be used for additional blood collection for MBC and DNA analyses. This second method will use venipuncture to collect ~6-10 cc of whole blood (except in students younger than 5 years in whom we will collect between 3-5cc). The possible complications of phlebotomy/venipuncture include pain, small local hematoma formation, bleeding and infection. However, this method of blood collection and testing is widely used by millions individuals daily in the United States with minimal complications, including IDD subjects. Phlebotomy will be conducted by a team specially trained in working with IDD subjects to minimize risk.

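### The staff inclusion criteria list having less than one month of employment left, which contradicts the stated staff population and up to 36 months of antibody sampling

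*Protocol*

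**What the plan says.** The staff row of the table in Protocol section 2.2 has four inclusion items: an age range of 18 to 72, ability to consent, "Anticipated duration of remaining employment less than 1 month (e.g. retiring", and willingness to have both PCR and antibody tests. The staff exclusion cell is separate and covers only medical reasons against a swab or a blood draw. Section 3.1 then states: "Selection will occur as a function of the criteria above".

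Section 2.1 describes a different population: "All staff and students at Mary Cariola Center (MCC) are eligible for this study". It counts 500 on-site staff and 450 students and says of enrolment overall, "although we expect around 70% enrollment". For employees in particular it expects at least 50% to consent to testing. It also says that nobody is excluded by age, subject to the ages of those who attend, live or work at the school, and gives a staff age range of 18 to 75.

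Antibody follow-up is long. Goal 2 measures IgG in students and staff at baseline "and then every four weeks by fingerstick for up to 36 months". Section 4.1 plans fingersticks for students and employees at the first sampling visit and "monthly thereafter for up to 36 months", with venous draws at the start and "subsequently, every six months for up to 36 months". The clinical serology text in section 1.4 agrees: "Serum will be collected upon enrollment and then every 6 months for the duration of the study period". Section 4.4 pays staff at monthly fingerstick visits for as long as they are enrolled.

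**The concern.** A criterion in an inclusion list must be met for a person to enter. Taken at its word, this one turns away every staff member who expects to stay a month or longer. Those are the people whom sections 1.4, 2.1, 4.1 and 4.4 plan to follow.

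What is at stake is the definition of the staff cohort. The SAP plans descriptive infection rates and immunity levels in students and staff, and defines no staff population of its own that could override the table. Protocol section 9 asks for a CONSORT diagram and a table of protocol deviations, and both need a stated eligibility rule. Against the literal text, any enrolled staff member expecting to stay a month or more would be an eligibility deviation.

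**Working it through.** **Position of the item.** It stands third of four in the staff inclusion list, between ability to consent and willingness to be tested, both of which are genuine inclusion items. The exclusion cell reads as complete. No other section restates or corrects the item.

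**Expected staff numbers (section 2.1).**
- At the overall rate: 0.70 × 500 = 350 staff.
- At the staff-specific minimum for testing: 0.50 × 500 = 250 staff.

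The documents do not say how many staff are near departure. Neither figure is compatible with a cohort made up only of people in their last month of work.

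**Scheduled samples over the 36-month maximum, counting baseline.**
- Venous, every 6 months: 36/6 + 1 = 7.
- Fingerstick, monthly (section 4.1): 36 + 1 = 37.
- Fingerstick, every 4 weeks (Goal 2): 36 months is about 36 × 30.4375 = 1,095.75 days; 1,095.75/28 = 39.1, so 39 + 1 = 40.

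**Samples under the literal rule.** Assume a 30-day month, so that less than one month means days 0 to 29, and assume that follow-up ends with employment. The documents state neither.
- Venous: day 0 only = 1.
- Fingerstick, monthly: day 0 only = 1.
- Fingerstick, every 4 weeks: day 0, and day 28 if still employed = 1 to 2.
- PCR every 14 days: days 0, 14 and 28 = 3. PCR every 5 days: days 0, 5, 10, 15, 20 and 25 = 6.

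Some repeat PCR testing would therefore still fit. The conflict is with the antibody follow-up and the stated population.

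**Consequence for the decay model.** Goal 2 fits a curve in which each person has their own peak level and decay rate. One sample says nothing about a person's own decay, and two samples 28 days apart say very little.

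**A less demanding comparison.** 36 months is a maximum. Section 1.4 budgets 1,680 staff serology tests at 70% enrolment, which is 1,680/350 = 4.8 per person. The literal rule gives 1.

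**Age.** Under the table's limit of 72, staff aged 73 to 75 are ineligible; under section 2.1 they are eligible. Their number is not given.

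**The case against.** The strongest reply is that this is a self-evident slip. The example of retirement belongs to an exclusion criterion, nobody would run a 36-month serology study in departing staff, and the planned staff outputs are descriptive. That is fair and limits the severity. It does not remove the point, because recognising the slip does not reveal which rule was used at screening.

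Three further objections stand in whole or in part.
- **The visit counts.** They depend on follow-up ending at departure and on the choice of schedule. Section 4.1 allows some home visits for testing, and section 1.4 gives 200 subjects for the four-weekly research assay. The counts are therefore shown as ranges and only illustrate a contradiction that the text already establishes.
- **Later conflicts.** A reader might infer that any correction would still contradict section 2.1 and limit the enrolment route to mandated weekly testing in section 4.1. The documents do not support that. Deleting the item would agree with section 2.1 and leave the testing route untouched. Keeping an employment limit would be ordinary narrowing of a source population, as the swab and phlebotomy contraindications already are. Section 4.1 presents enrolment as one way to meet the testing policy and does not promise it to every unvaccinated employee.
- **Evidence about use.** A reader might infer that the literal rule was not applied, because a repeat questionnaire goes to all current participants and the six-monthly adult draws are marked as completed. Neither settles it. Questionnaires go to staff or to parents of students, and adults include students aged 18 to 21.

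**Conclusion.** The inclusion item is wrong as written, and section 3.1 makes it operative. It contradicts the stated staff population and the planned antibody follow-up of staff. The likely explanations are an exclusion placed in the wrong column, a reversed inequality, or an item that should not be there. The documents do not say which, and they do not show which rule was applied to enrolled staff.

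Under the stated assumptions, the literal rule leaves 1 of up to 7 venous draws and 1 to 2 of up to 37 to 40 fingersticks per staff member.

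A reader might go further and infer that the enrolled staff were in fact only people about to leave, or that the staff results are biased. Nothing in the documents shows either, and no harm to safety or to a named estimate is shown. The finding is an eligibility rule that needs correcting and a staff cohort that is not clearly defined. The age mismatch is a separate, smaller inconsistency that stands however the employment item is resolved.

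**What to change.** 1. The sponsor confirms the intended employment rule and corrects the staff row in one of three ways: move the item to the exclusion column; reverse the inequality and reword the example; or delete the item.
2. Record which rule was applied to staff already enrolled, including any who were near departure, and check whether anyone falls outside the corrected rule.
3. Only if an employment limit is kept, qualify the statement in section 2.1 that all staff are eligible.
4. Separately, reconcile the table's staff age range of 18 to 72 with section 2.1, which has no age exclusions and staff aged 18 to 75.

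The cost is one corrected table row, at most a sentence or two in section 2.1, and a short record with a check of enrolled staff. No study procedure is added.
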